Any surgery on the esophagus, stomach or duodenum may result in injury to the vagus nerve that is responsible for many sensory and motor (muscle) responses of the intestine. In health, the vagus nerve sends neurotransmitter impulses to the smooth muscle of the stomach that result in contraction and forward propulsion of gastric contents. If the vagus nerve is injured by trauma or during surgery, gastric emptying may be reduced. Symptoms of postoperative gastroparesis may develop immediately, or months to years, after a surgery is performed. The vagus nerve helps manage the complex processes in the digestive tract, including signaling the muscles in the stomach to contract and push food into the small intestine. A damaged vagus nerve cannot send signals normally to the stomach muscles. This may cause food to remain in the stomach longer, rather than move normally into the small intestine to be digested. In the stomach longer, rather than move normally into the small intestine to be digested.

Several medications are used to treat gastroparesis and CUNV to control the symptoms specially nausea and vomiting such as the 5-HT3 antagonist (e.g. ondansetron) or D2 receptor antagonist (e.g. Promethazine). ¹⁷ Other medications stimulate the stomach muscles and help with digestion with prokinetics. These include metoclopramide, erythromycin and domperidone. ^{1,18} However, the drugs can cause side effects.

When gastroparesis does not respond to standard medical management, including drugs and dietary changes, the condition is said to refractory. Gastric Electrical Stimulation (GES) uses a device, surgically implanted in the abdomen, to deliver mild electrical pulses to the nerves and smooth muscle of the lower part of the stomach. This procedure reduces the nausea and vomiting and may be considered for compassionate treatment in patients with refractory symptoms, particularly in patients with persisting symptoms and GES.¹⁹

The vagus nerve plays a key role in regulation of nausea and vomiting, and there is evidence of vagus afferent effects on nociception, which suggests that electrical stimulation modulates nauseas and vomiting. The current proof of concept study explores the possibility that non-invasive vagus nerve stimulation (nVNS) could have clinical effects similar those of an implanted gastric electrical stimulation device in patients with symptoms of gastroparesis. GES report some complications, the main one being the infections of subcutaneous pocket, inflammation over implant site, device migration/erosion, lead penetration, extra-abdominal pain, seroma and hematoma. Less common complications include erosions of the abdominal wall by the device, penetration of the leads through the gastric wall, or tangling of wires in the generator pocket and formation of adhesions. GES is relatively expensive treatment with the high cost of the device and for the surgical procedure. ²⁰⁻²²

gammaCore (nVNS) is the first non-invasive, handheld medical device²³ applied on the side of the neck and sends gentle, patented mild electrical stimulation through the skin to activate the vagus nerve. nVNS offers a potential alternative to GES that could eliminate significant risks of injury or illness or identify likely responders to implantable neurostimulator including implanted VNS (iVNS). nVNS could provide a more effective and safer alternative to the use of traditional rescue medications.

nVNS primarily stimulates myelinated sensory afferent vagus nerve fibers as they ascend through the neck in the carotid sheath. nVNS has been cleared for the acute and preventive treatment of migraine and the acute and preventive treatment of cluster headache by the Food and Drug Administration (FDA) and is also CE marked and used in several all forms of primary headache. ^{24, 25}

The hypothesis of the pilot study is that nVNS will result in relief of nausea by modulation of vagal nerve activity.

- **2. Objectives** (include all primary and secondary objectives)
- The principal objective of this open label pilot study is to evaluate whether acute treatment
 of nausea exacerbations with nVNS will be effective in reducing the use of rescue
 medications.
- Secondary objectives of this study include:
 - o Determine the nature and incidence of adverse effects.

- Exploratory objectives
 - o Determination of the effects of nVNS (or correlation with response) use on:
 - Patient Assessment of Upper Gastrointestinal Symptom Severity Index (PAGI-SYM) and the Gastrointestinal Symptom Rating Scale (GSRS).
 - Depression and anxiety using the Beck Depression Inventory and State-Trait Anxiety Scores.
 - Frequency of migraines and headaches (since many patients with gastroparesis have concomitant migraine) defined as, 'migraine day'= a migraine headache occurring in a 24-hour period, and a 'headache day'= any headache occurring in a single calendar day.
 - Autonomic symptoms as determined by the COMPASS-31 score.
- **3. Background** (briefly describe pre-clinical and clinical data, current experience with procedures, drug or device, and any other relevant information to justify the research)

Chronic nausea and vomiting are the clinical hallmarks of gastroparesis and Chronic Unexplained Nausea and Vomiting or CUNV (very similar to Functional Dyspepsia of the postprandial subtype, FD-PPS, by Rome criteria) or related disorders and in most cases, are constant and daily symptoms. However, in addition, the majority of these patients also experience periodic exacerbations of these symptoms either on a daily basis or several times in a week. These exacerbations require them to use "rescue" medications such as 5-HT3 antagonists (e.g. ondansetron) or D2 receptor antagonists (e.g. Promethazine). These are only partially effective at best and often associated with adverse effects. Our hypothesis is that nVNS may provide a more effective and safer alternative to the use of traditional rescue medications. We therefore believe that while nVNS may not necessarily be a stand-alone treatment for gastroparesis, it has the potential for meeting a large unmet "niche" need in this condition.

4. Study Procedures

Patients who appear to be eligible after chart review and completion of standard of care tests and procedures for gastroparesis, CUNV or related disorders will be invited to undergo screening for study. Patients considered by the clinical center investigator as likely to be eligible for participation in the trial may be consented, registered and screened at a visit that is part of the ongoing clinical care of the patient.

After informed consent is obtained, patients will fill out a validated symptom-based questionnaires and assessment daily.

Visit schedule

- At least 2 weeks of pre-treatment observation (screening).
- 8 weeks of treatment
- 2 weeks of post-treatment observation.
- Length of recruitment: 9 months

1. Screening visit and baseline data collection

Study participants will come from the patient rosters of study physicians. Patients who appear to be eligible after chart review and completion of standard of care test and procedures will be invited to undergo screening for the trial. Patients considered by the clinical center investigator as likely to be eligible for participation in the trial may be consented, registered and screened at a visit that is a part of the ongoing clinical care of the patient.

An open label pilot study to be conducted at Johns Hopkins Bayview Medical Center over 9 months to evaluate with nVNS for the symptomatic exacerbations of nauseas in patients with gastroparesis or CUNV. Approximately 30 patients will be enrolled in the study. Inclusion criteria will include patients 18 years or older with symptomatic nausea, vomiting and other symptoms suggestive of chronic nausea and vomiting of presumed gastric origin (Gastroparesis or CUNV). All the participants will come from the patient roster of the study physicians from the Division of Gastroenterology, Department of medicine: [name] (Principal Investigator), and [name].

In order to minimize the need for research-only in-person visits, telemedicine visits may be substituted for in person clinical trial visits or portions of clinical trial visits where determined to be appropriate and where determined by the investigator not to increase the participants risks. Prior to initiating telemedicine for study visits the study team will explain to the participant, what a telemedicine visit entails and confirm that the study participant is in agreement and able to proceed with this method. Telemedicine acknowledgement will be obtained in accordance with the Guidance for Use of Telemedicine in Research. In the event telemedicine is not deemed feasible, the study visit will proceed as an in-person visit. Telemedicine visits will be conducted using HIPAA compliant method approved by the Health System and within licensing restrictions

Revisions to the informed consent process are being permanently adopted for this research. Teleconsent will be used as opposed to in person consenting where possible to reduce unnecessary in person encounters specifically for a consent procedure. In the event teleconsent is utilized, participants will be provided with a copy of the Informed Consent prior to the teleconsent meeting either via email, fax, mail or previously provided during an in person visit.

Participants will be given adequate time to consider the research study and ask questions prior to signing the consent form. The consent designee must verify the participant physically signed the consent document by either viewing via video conference, obtaining a photo of the signed consent document; or obtaining verbal confirmation from the participant that he/she signed the consent form or agreed to participate electronically. The participant will sign and date/time the informed consent document. The document is then mailed, emailed or faxed to the consent designee. The participant will be asked to return the original signed document on their first in person visit. If the Informed Consent form is mailed to the consent designee by the participant the study coordinator will sign the copy, which they possess after the participant has acknowledged signature on their copy. Once the original is received by the consent designee the copies will be

attached to make a single document. In all other instances, once received, the research coordinator signs, dates/times the informed consent document.

At the time of the first clinical encounter post teleconsent, research coordinator will review any additional study participant questions and discuss the risks, benefits and alternatives of the study in full detail, completing the physician/mid-level component of the consent process. After the Informed Consent process is completed, a study team member will file the consent document in EPIC. The entire consent document is also then filed in the research record.

Only patients who are sufficiently proficient in English will be recruited for this study. All potential study candidates will be able to obtain a consent form in advance and review it at their own time, as needed. All contact information for the lead study coordinator and the study PI will be given to the potential candidate when they are given a copy of the consent form.

As part of the screening process for the trial, the patient must have a diagnosis of gastroparesis or CUNV with delayed gastric emptying documented by gastric emptying scintigraphy (4-hour emptying after a low-fat meal with any combination of 2- and 4-hour retention of >60% and 10% respectively) and ongoing symptoms such as: nausea, vomiting, abdominal pain, etc. for at least 3 months without any other obvious cause. Patients must also have a normal upper endoscopy or standard radiography, to rule out other potential causes of symptoms such as mechanical obstruction, inflammatory or other structural lesions of the GI tract or non-gastrointestinal causes.

Recording of screening data on trial forms may not start until the patient has signed the informed consent form (ICF). Screening and baseline data collection procedures will include questionnaires, urine pregnancy test, 12 lead EKG, and review of the patient's medical chart.

All participants who sign the ICF will be registered in the trial database. Each participant who starts screening will be accounted for at the end of the screening, as either success or a screening failure. Screening failure is defined as a participant who signed the consent form and was registered in the trial data system, but is found to be ineligible prior to start of treatment. Screening failures include patients who meet medical eligibility criteria but change their mind and do not consent to participate in the trial. The reason for screening failure will be recorded and keyed into the database.

Screening visit:

The patient will undergo a medical history to identify other illness and contraindications for participations such as use of narcotics for more than 3 days per week, previous surgery of the upper gastrointestinal tract, history of prolonged QT interval or clinical significant arrhythmia, etc.

In addition, the patient will be provided with the questionnaires and will be administered on a daily basis for up two weeks before treatment with following questionnaires (delivered electronically):

- Gastroparesis Cardinal Symptom Index Daily Diary (GCSI-DD)

- Rescue medication uses daily diary- number of pills and type. Rescue medications that will be allowed for this trial are ondansetron, promethazine and prochlorperazine.
- Migraine and headache daily diary
- Gastrointestinal Symptom Rating Scale (GSRS)
- Patient Assessment of Upper Gastrointestinal Symptom Severity Index (PAGI-SYM)
- Beck Depression Inventory (BDI-II)
- State- Trait Anxiety Inventory (STAI)
- Average weekly frequency of migraine headaches for the last 4 week period
- COMPASS-31 score.

Anthropomorphic assessments (body weight, body height, body mass index [BMI]. Pregnancy test results that need to be recorded from chart review or obtained as part of the screening and EKG to rule out any abnormal baseline electrocardiogram such as second and third degree heart block, atrial fibrillation, atrial flutter, recent history of ventricular tachycardia or ventricular fibrillation, or clinically significant premature ventricular contraction, history of prolonged QT interval or a history of clinically significant arrhythmia.

Data will be captured on REDCAP and stored on the secure Hopkins server for this purpose.

2. Treatment Start Visit

At this visit, the patient will receive the gammaCore (nVNS) device and a video instruction will be use to explain how to properly handle the device. Treatment can only start after eligibility has been fully checked and all data collected at screening have been keyed into the trial database. Women of childbearing potential must have a negative urine pregnancy test.

After eligibility is confirmed with the clinical center staff the treatment can begin. The date of starting treatment is the start (ZERO) time for the timing of follow-up visits.

Frequency and duration of nVNS treatment.

The treatment will be self-administered using nVNS and will be applied for 8 weeks; 4 weeks will be used on one side of the neck and other 4 weeks in the contralateral side. A member of the study will provide the proper training on the correct use of nVNS. The patient will be instructed to use the nVNS in place of the rescue medications. When the nauseas gets bad enough that they feel to use a rescue medication they will first use the device on one side of the neck for two 2minute stimulations and wait fifteen minutes to check if the stimulation works. If this does not help either, they will stimulate with an additional 2 stimulations and wait for another fifteen minutes. If there is no improvement rescue medication will be used. nVNS can be used up to, but no more than, 8 times a day.

3. Follow-up Visits

Patients will return for follow-up visits at 4 and 10 weeks after treatment initiation. The specific

procedures to be completed at each of the follow-up visits are:

- Week 4 visit: The following questionnaires should be completed and collected:
 - Gastroparesis Cardinal Symptom Index Daily Diary (GCSI-DD)
 - Rescue medication uses daily diary- number of pills and type
 - Migraine and headache daily diary
 - Gastrointestinal Symptom Rating Scale (GSRS)
 - Patient Assessment of Upper Gastrointestinal Symptom Severity Index (PAGI-SYM)
 - Beck Depression Inventory (BDI-II)
 - State- Trait Anxiety Inventory (STAI)
 - Average weekly frequency of migraine for the last 4 week period
 - COMPASS-31 score.
 - Global patient impression (GCPI) questionnaire.

Laboratory test results that need to be collected are EKG and urine pregnancy test. Review study of adverse events will be addressed.

- Week 8 visit: This will be the end of study visit. A medical history, including side effect or symptom profile will be collected. The following questionnaires should be completed and collected:
 - Gastroparesis Cardinal Symptom Index Daily Diary (GCSI-DD)
 - Rescue medication uses daily diary- number of pills and type
 - Migraine and headache daily diary
 - Gastrointestinal Symptom Rating Scale (GSRS)
 - Patient Assessment of Upper Gastrointestinal Symptom Severity Index (PAGI-SYM)
 - Beck Depression Inventory (BDI-II)
 - State- Trait Anxiety Inventory (STAI)
 - COMPASS-31 score.
 - Global patient impression (GCPI) questionnaire.
- Week 10 visit: This will be the end of study visit. A medical history, including side effect or symptom profile will be collected. The following questionnaires should be completed and collected:
 - Gastroparesis Cardinal Symptom Index Daily Diary (GCSI-DD)
 - Rescue medication uses daily diary- number of pills and type
 - Migraine and headache daily diary
 - Gastrointestinal Symptom Rating Scale (GSRS)
 - Patient Assessment of Upper Gastrointestinal Symptom Severity Index (PAGI-SYM)
 - Beck Depression Inventory (BDI-II)
 - State- Trait Anxiety Inventory (STAI)
 - COMPASS-31 score.
 - Global patient impression (GCPI) questionnaire.

	Screening & GammaCore treatment Visits (Weeks)		Follow-up Visits: Weeks from start of treatment		
	Screening (0)	Treatment initiation (2)	4	8	10
Consent	X				
Baseline medical	X				
history					
GCSI-DD	X		X	X	X
Rescue Medication Daily Diary	X		X	X	X
Migraine and Headache Daily Diary	X		X	X	X
Collection of GCSI- DD		X	X	X	X
Collection of Rescue Medication Daily Diary		X	X	X	X
Collection of Migraine and Headache Daily Diary		X	X	X	X
PAGI-SYM questionnaire	X		X	X	X
GSRS questionnaire	X		X	X	X
Beck Depression Inventory-II	X		X X	X X	X X
State Trait Anxiety Inventory	X		X	X	X
COMPASS 31-score			X	X	X
Noninvasive Vagal Neural Stimulation (VNS) device dispensed		X			
Follow-up medical history, including review of adverse events			X		X
12-lead EKG	X		X		
Urine pregnancy test	X		X		

Specific Tests and Questionnaires

- Pregnancy test: Women of childbearing potential must have a negative urine pregnancy test.
- 12-lead EKG: To rule out any abnormal baseline electrocardiogram such as second and third degree heart block, atrial fibrillation, atrial flutter, recent history of ventricular tachycardia or ventricular fibrillation, or clinically significant premature ventricular contraction, history of prolonged QT interval or a history of clinically significant arrhythmia.
- Gastroparesis Cardinal Symptom Index (GCSI) Daily Diary:²⁶ Consists of five core symptoms (nausea, vomiting, early satiety, postprandial fullness, upper abdominal pain).
 Each night, participants grade the severity of symptoms over the prior 24 hours. The GCSI-DD core symptom composite score (an average of the five core symptoms) is designed to detect clinical improvement in symptoms of gastroparesis and to be used as a PRO outcome for clinical trials.
- Rescue medication daily diary: Must contain the name of the antiemetic medications, dosage, frequency and number of pills during the day.
- Gastrointestinal Symptom Rating Scale (GSRS): ²⁷ The GSRS is a disease-specific instrument of 15 items combined into five symptom clusters depicting Reflux, Abdominal pain, Indigestion, Diarrhea, and Constipation. The GSRS has a seven-point graded Likert-type scale where 1 represents the absence of troublesome symptoms and 7 represents very troublesome symptoms. The reliability and validity of the GSRS are well-documented and normative values for a general population are available.
- Patient Assessment of Upper Gastrointestinal Disorders-Symptoms (PAGI-SYM): ²⁸ The self-reported questionnaire is composed of 20 items and 6 subscales. The severity of each symptom item over a 2-week recall period is scored from 0 (none or absent) to 5 (very severe). The GCSI, a 9-symptom survey relevant to gastroparesis stratified in 3 subscales nausea/vomiting, fullness/early satiety, and bloating, is contained in the PAGI-SYM. The GCSI correlates with patient severity ratings and is responsive to changes in overall symptoms. Two additional items for constipation and diarrhea also will be recorded and scored and their main symptom will be determined.
- Beck Depression Inventory, Second Edition (BDI-II): ²⁹ The BDI-II is a commonly used, reliable 21-item self-report measure designated to assess for depression.
- State Trait Anxiety Inventory: ³⁰ The STAI is a 40-item self-report measure designed to assess both situational and characterological anxiety. This measure provides two subscale scores (State and Trait) and has been shown to exhibit good reliability and internal consistency.

- Migraine and headache daily diary: is going to record various aspects of headache or migraine attacks, monitor the frequency, type, duration, severity, symptoms, possible triggers and track medication use.
- Migraine Frequency: This will be obtained from the Migraine and headache daily diary.
- COMPASS-31:³¹ Is a self-report measure for assessing symptoms of dysautonomia. Scale contains 31 questions in six domains, yielding an overall autonomic symptom score from 0 to 100. The domains are orthostatic intolerance (4 questions), vasomotor (3 questions), secretomotor (4 questions), pupillomotor (5 questions), bladder (3 questions), and gastrointestinal (including diarrhea, constipation, and gastroparesis, 12 questions). For each question there is a numeric rating based on factors such as site, consistency, severity, frequency, or trends.

Recruitments Procedures:

Individuals Responsible for Approaching Participants:

Prospective participants will be approached by their own physicians who are study team members Recruitment will take place while the potential participants are present for clinic appointments. Potential participants will be informed that participation is voluntary and that their care at Johns Hopkins will not be affected if they considered not participating it this study.

How Privacy Issues will be addressed:

The study team member will approach the participants when they are alone in the exam rooms to ensure privacy so that others cannot hear the conversation between the participant and study team members. After ensuring that sufficient privacy is achieved and that the potential subjects are at ease and comfortable with their surroundings, the consent designee will obtain informed consent to enter the study and explain the study procedures verbally and encourage the potential subjects to ask questions.

The questionnaires will also be filled out during the treatment and during the 2 weeks after nVNS treatment has been completed. All questionnaires are short and easy to fill out with multiple-choice type responses. Adverse events (AEs) will also diarized.

All participants who sign the ICF will be registered in the trial database. Each participant who starts screening must be accounted for at the end of the screening, as either a screening success or a screening failure. A screening failure is defined and a participant who signed the consent form and was registered in the nVNS trial data system, but is found to be ineligible prior to start of treatment; screening failures include patients who meet medical eligibility criteria but change their mind and do not consent to participate in the trial. The reason for screening failure will be recorded and keyed into the trial database.

5. Inclusion/Exclusion Criteria

Inclusion criteria

- Age 15 years or older at registration.
- Diagnosis of gastroparesis as documented by gastric emptying scintigraphy (4-hour emptying after a low-fat meal with any combination of 2- and 4-hour retention of >60% and 10%, respectively), or Chronic Unexplained Nausea and Vomiting (CUNV).
- Ongoing symptoms (i.e. Nausea and vomiting, bloating, and abdominal pain) with a nausea score of 3 or more on the PAGI-SYM scale at baseline (moderate to severe nausea).
- Exclusion of other causes of symptoms such as mechanical gastrointestinal obstruction, uncontrolled esophagitis, peptic ulcer disease, etc. By standard radiographic or endoscopic tests.
- Use of the following medications on an as-needed basis: ondansetron, promethazine or prochlorperazine but no more than four times a day.

Exclusion criteria

- Another active disorder, which could explain symptoms in the opinion of the investigator.
- Age < than 15 years.
- Pregnancy or nursing.
- A previous surgery of the upper gastrointestinal tract, including vagotomy.
- Use of narcotics more than 3 days per week.
- History of prolonged QT interval or a history of clinically significant arrhythmia.
- Abnormal baseline ECG (e.g. Second- and third-degree heart block, atrial fibrillation, atrial flutter, recent history of ventricular tachycardia or ventricular fibrillation, or clinically significant premature ventricular contraction).
- Previous bilateral or right cervical vagotomy.
- Uncontrolled high blood pressure.
- Currently implanted with an electrical and/or neurostimulator device, including but not limited to cardiac pacemaker or defibrillator, vagal neurostimulator, deep brain stimulator, spinal stimulator, bone growth stimulator, or cochlear implant.
- History of carotid endarterectomy or vascular neck surgery on the right side.
- Implanted with metal cervical spine hardware or has a metallic implant near the gammaCore stimulation site.
- Any other condition, which in the opinion of the investigator would impede compliance or hinder the completion of the study.
- Failure to give informed consent.

6. **Drugs/ Substances/ Devices**

gammaCore Sapphire (nVNS) ²³⁻²⁵

Description:

nVNS is a multi-use, hand-held, rechargeable, portable device consisting of a rechargeable battery, signal-generating and -amplifying electronics, and a control button for the patient to control the signal amplitude. The device provides visible (display) and audible (beep) feedback on the device and stimulation status. A pair of stainless steel surfaces, which are the skin contact surfaces ("stimulation surfaces"), allow the delivery of a proprietary electrical signal. The patient applies electroCore-approved gel to the stimulation surfaces to maintain an uninterrupted conductive path from the stimulation surfaces to the skin on the neck. Tubes of electroCore-approved gel are provided with each unit and refill kit for this purpose. The stimulation surfaces are capped when not in use.

7. Study Statistics

Data analysis will be performed at Mayo Clinic Scottsdale, Arizona by [name], ([contact]). This site will no recruit participants.

Johns Hopkins will serve as coordinating center, responsible for overall data management, monitoring and communication among both sites, and general oversight of the conduct of this protocol.

Outcome measures

Primary: The primary outcome measure is the average daily use of rescue medications for exacerbation of nausea/vomiting.

Sample size justification

- Primary endpoint: Improvement in nausea control, as defined by a 50% reduction n the number of weekly doses of rescue medications, compared with baseline.
- Total of 45 patients. This is a pilot study to assess the strength of the signal (improvement) with peripheral VNS for nausea. Since there is evidence that the left and right vagus may have different pathways within the CNS, with the left side being dominant in innervation of center involved in food aversion and nausea (Cell 175, 665–678, 2018), we are proposing to study three groups as follows
 - Group 1; Start with left sided stimulation 15 patients
 - Group 2. Start with right sided stimulation 15 patients
 - Group 3. Both sided stimulation 15 patients
- Our assumptions are as follows, in terms of the number of patients improving in each group

Group 1: 4/15 Group 2: 11/15 Group 3: 7/15

If these assumptions are true, the type I error will be < 0.05

8. Risks³²⁻³⁴

The adverse reactions observed in nVNS studies include:

- i. Shortness of breath (dyspnea), hoarseness, or change in voice during treatment.
- ii. Muscle twitching, discomfort, or pain during stimulation.
- iii. Change in taste (dysgeusia).

These first three reactions resolved after treatment was completed.

- iv. Local skin irritation/inflammation.
- v. Any progression of headache symptoms.

Adverse reactions not seen in the studies, but associated with implanted vagal nerve stimulation devices include:

- vi. Tingling, pricking, or a feeling of "pins and needles" on the skin where the device is applied (paresthesia or dysaesthesia) lasting beyond the treatment period.
- vii. Fainting (syncope), light-headedness, and/or dizziness.
- viii. Sweating.
- ix. Fatigue, depressed mood.
- x. Tinnitus.
- xi. Diarrhea.
- xii. Abnormal heart rhythm.

Adverse events will be evaluated in every follow-up visit. A form of Adverse Event will be completed if the candidate complains of any symptoms, sign, abnormal assessment or any combination of these. An adverse event can be expected side effect that is of a serious nature, or an unexpected side effect/event regardless of severity.

This study will monitor and report adverse events to ensure patient safety to IRB and FDA. Signs and symptoms associated with the adverse event will be graded as to severity by the clinical site staff as mild, moderate, or sever using Version 5.0 of the National Cancer Institute's Common Terminology Criteria for Adverse Events (CTCAE).

9. Benefits

Description of the probable benefits for the participant and for society.

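### Regular nausea therapy is neither held stable, scheduled for recording nor handled in the analysis, so its changes are attributed to the device in the change from baseline

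*Combined protocol and SAP*

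**What the plan says.** **Entry.** Section 4 invites "Patients who appear to be eligible after chart review and completion of standard of care tests and procedures for gastroparesis, CUNV or related disorders"; those judged likely to be eligible "may be consented, registered and screened at a visit that is part of the ongoing clinical care of the patient". They come from the study physicians' own rosters and are approached at clinic appointments by treating physicians who belong to the study team.

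**Background therapy.** The introductory section, before section 2, acknowledges regular treatment: "Other medications stimulate the stomach muscles and help with digestion with prokinetics. These include metoclopramide, erythromycin and domperidone". Section 3 adds that the device may not be a stand-alone treatment.

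**Medication rules.** Section 5 has two: as-needed use of ondansetron, promethazine or prochlorperazine at most four times a day, and exclusion for narcotics on more than 3 days a week. Section 4 names the same three drugs as the permitted rescue medication.

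**Medication records.** The rescue diary covers antiemetics, and the headache diary covers medication taken for headache or migraine. The visit table has no row for concomitant medication.

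**Endpoint and design.** Section 7 gives average daily rescue use as the primary outcome. Under sample size it gives a primary endpoint: "Improvement in nausea control, as defined by a 50% reduction n the number of weekly doses of rescue medications, compared with baseline". The baseline is at least 2 weeks of observation, followed by "8 weeks of treatment" and "2 weeks of post-treatment observation". The study is open label, and all three groups in section 7 are stimulated: left first, right first, or both sides.

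**The concern.** A within-patient change from baseline in an open-label study without an unstimulated group has no internal means of separating the device from anything else that changes over the same weeks. Regular nausea therapy is the most direct competitor, because it acts on the symptom that triggers rescue use. From the introduction onward, the document neither requires that therapy to be stable before or during the study, nor schedules a record of changes, nor says how a patient with a change is analysed.

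At stake is the purpose that section 7 gives the pilot, which is to gauge the strength of the signal. An unrecorded co-intervention moves that signal by an unknown amount, in a direction that depends on whether therapy was stepped up or down.

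**Working it through.** **1. The plan's own figure.** Section 7 assumes 4/15, 11/15 and 7/15 improving and says the type I error is then below 0.05. Read as a p-value for those counts, this reproduces. The pooled rate is (4 + 11 + 7)/45 = 22/45 = 48.9%, so 7.33 improvers are expected per group. Pearson chi-square = [(4 - 7.33)² + (11 - 7.33)² + (7 - 7.33)²] / [15 × (22/45) × (23/45)] = 24.67/3.748 = 6.58 on 2 df, p = 0.037. The exact p is 0.046. The present point does not depend on this figure; it uses only the assumed rates 22/45 and 4/15.

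**2. One patient followed through the rules.** Suppose a patient has a stable 2-week baseline, starts metoclopramide in week 1 of treatment and then halves weekly ondansetron doses.
- Section 5: eligible, since neither medication rule concerns a prokinetic.
- Section 4 diaries and visit table: no scheduled item asks about the new drug.
- Section 7: the 50% criterion is met and nothing qualifies it.

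The patient is a responder, and the response is credited to the device. Conversely, a patient who stops a prokinetic and therefore keeps the same rescue use is a non-responder, even if the device helped.

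**3. Illustrative size.** The documents give no rate of therapy change, so these inputs are assumptions:
- f, the fraction who start or increase regular nausea therapy: 10% to 25%;
- r, the fraction of those who meet the 50% criterion for that reason alone: 50%;
- p, the response rate without such changes: 22/45 (pooled) or 4/15 (lowest group), from section 7;
- a therapy change is unrelated to whether the patient would have responded anyway.

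Only patients who would not otherwise respond can add to the count, so the increase is f × r × (1 - p).

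| p | f = 10% | f = 25% |
|---|---|---|
| 22/45 | 0.10 × 0.5 × 23/45 = 2.6 points | 0.25 × 0.5 × 23/45 = 6.4 points |
| 4/15 | 0.10 × 0.5 × 11/15 = 3.7 points | 0.25 × 0.5 × 11/15 = 9.2 points |

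At the pooled rate this is 45 × 0.0256 = 1.2 to 45 × 0.0639 = 2.9 patients. With the roughly 30 patients stated in section 4 instead of the 45 in section 7, it is 0.8 to 1.9. The percentage points do not depend on which total is right.

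With f from 10% to 30% and r from 25% to 100%, the apparent rate runs from 50.2% to 64.2% when p = 22/45, and from 28.5% to 48.7% when p = 4/15.

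**4. The opposite direction.** If the same 10-25% instead step down, and half of those who would have responded lose their response, the fall is f × 0.5 × p. At 22/45 this is 0.05 × 0.489 = 2.4 to 0.125 × 0.489 = 6.1 points. The net effect depends on the mix, which the plan does not record.

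**The case against.** The strongest reply is that this is a self-described pilot in which uncontrolled attribution is inherent, and background therapy is one unquantified source among several. That limits the weight of the point. It does not remove it, because this source can be recorded cheaply and the others mostly cannot.

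Four stronger readings are tempting, and the documents do not support them.

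- *Entry at a clinic visit after work-up is when therapy is likely to change.* No section says so. Symptoms must have lasted at least 3 months, patients come from existing rosters, and they already use as-needed antiemetics, which fits established care equally well. None of this guarantees stability.
- *The bias favours the device.* Only starts and increases do so. Stepping down hides benefit, and a drug started before the run-in can lower baseline rescue use and make a 50% reduction harder to reach.
- *The information is lost for good.* Section 4 provides for chart review and medical history, the single recruiting site has an electronic record, and the rescue diary asks for the names of antiemetics. Partial recovery is plausible; what is missing is a scheduled record and a prespecified use of it.
- *The three-group comparison is equally compromised.* It is affected only if changes differ by group. No allocation method is described, so balance cannot be assumed, but imbalance cannot be asserted either.

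The 2-week post-treatment diary might hint at whether improvement outlasts the device, but no analysis of it is planned.

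**Conclusion.** The point holds for the change from baseline, on which the principal objective rests. As written, the plan classifies a patient whose rescue use falls because of a new prokinetic as a device responder. That is a wrong classification under the stated rules, not merely missing detail.

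The size is illustrative: 2.6-6.4 points at 22/45 and 3.7-9.2 points at 4/15, resting on an assumed 10-25% starting or increasing therapy, half of them crossing the 50% line because of it, and independence from the response they would otherwise have had. A reader might infer 5 to 12.5 points from f × r alone (0.10 × 0.5 to 0.25 × 0.5). That counts every such patient as an extra responder and ignores those who would have responded anyway, so it is an upper value under these assumptions. For scale, one patient in a group of 15 is 6.7 points. The net direction is not determined by the documents. The plan should be changed, given how little the change costs.

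**What to change.** 1. **Record.** Add a background nausea-medication field (drug; start, stop or change; date) to the existing screening, treatment-start and week 4, 8 and 10 forms.
2. **Section 5.** State a stability condition for regular nausea therapy before and during the run-in. Its length is for the investigators to set.
3. **Section 7, responder analysis.** Count as a non-responder any patient whose regular nausea therapy is started or increased during the run-in or the 8 weeks.
4. **Section 7, average daily use.** Keep all diary days in the main analysis. Setting aside days only after a start or increase would be asymmetric, and would leave a patient changed during the run-in with no outcome.
5. **Sensitivity.** Prespecify an analysis excluding patients with any change, in either direction.

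Treating physicians stay free to change therapy; only recording and classification are affected. The cost is one form field, a possible short delay in entry for some patients and a slightly lower response rate.
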